5.4 Withdrawals and Discontinuation of Treatment

In accordance with legal requirements and International Conference on Harmonisation (ICH) – Good Clinical Practice (GCP) guidelines, every subject has the right to refuse further participation in this trial at any time and without providing reasons (see also [Section 9.2](#)). A subject's participation is to be terminated immediately upon his/her request. The investigator should seek to obtain the reason and record this on the electronic case report form (eCRF) whenever possible. If,

at the time of refusal, a trial product has already been administered, the subject should also be advised to have an Early Termination visit performed (see section 7.13 Early Termination) and follow up on treatment related AEs.

In case of an SAE or development of a condition that would have met the trial safety-related exclusion criteria, the subject should be evaluated by the investigator. The investigator should use his/her discretion to determine whether the subject should continue treatment with the IP. Examples of SAEs that do not necessarily require discontinuation of treatment include but are not limited to a hospitalisation that is not related to the IP, for example removal of tonsils or polyps.

The reasons for discontinuation of treatment may be among others;

- HPA axis suppression is noted at Week 4
- inconsistency with inclusion / exclusion criteria
- intake of a prohibited medication(s)
- AE / SAE
- investigator's discretion

Subjects discontinued treatment due to a treatment-related AE will be monitored until the AE is resolved or until the medical condition of the subject is stable.

In case the treatment is discontinued all efforts should be made to have the subject completing the trial, or at least come in for the Week 8 visit, even if not being on treatment anymore.

Reasons for discontinuation of the trial may be among others;

- lost to follow-up,
- withdrawal of informed consent / informed assent
- pregnancy
- investigator's discretion
- sponsor's decision to terminate or suspend the trial
- termination of the trial by the Regulatory Authority.

5.5 Replacement Policy

After trial enrolment has been completed, subjects who prematurely discontinue the trial after randomisation can be replaced if necessary to ensure approximately 20 subjects are included in the PK population at Week 4.

6.0 TRIAL TREATMENTS

6.1 Investigational Product

MC2-01 cream is a combination product, calcipotriol and betamethasone dipropionate, administered as a cream formulation for topical administration. The MC2-01 cream is currently not a marketed product, which means that the product is still being tested and is not approved for sale. One concentration of the trial product will be studied: calcipotriol (50 micrograms) and betamethasone (0.64 mg/g, as dipropionate). The list of inactive ingredients present in MC2-01 cream is presented in the Investigator Brochure (37).

6.2 Dosing Regimen

Subjects are to apply the IP topically once daily, preferably in the evening, for 8 weeks. The subject should apply enough IP to treat the entire affected areas and rub in gently to ensure that the plaques are saturated with the medication. Up to 3 tubes of 60 gram will be dispensed for a treatment period of two weeks including the allowed visit window of 2 days.

The IP is applied to affected areas on the:

- scalp
- trunk (including the neck)
- limbs
 - arms (including the back of the hands)
 - legs (including the buttocks and the top of the feet).

Only affected areas are to be treated. The subjects should therefore not continue treatment on a skin area which has been cleared but treatment may be restarted in case of recurrence at the subjects discretion (Section 6.3).

The face, genitals, and intertriginous areas should not be treated with the IP. The first application is done at Day 0 under the supervision and instruction of the trial staff. Subsequent applications will be applied by the subject or by the parent(s) or legal guardian(s).

All subjects are instructed to apply IP in the morning on the day before the Week 2, Week 4 and Week 8 visits. On the day of these visits, the subjects should not apply any IP before the visit.

Subjects are to record the date and time of application in the subject dosing diary (with the assistance of the parent(s) or legal guardian(s), as needed). The treated area should not exceed 30% of the BSA.

In case an AE reported in one area of the body lead the investigator to the decision to discontinue treatment this will apply for treatment in general and not only to the area for which the AE was reported.

Detailed application instructions will be provided in the subject instructions.

6.3 Dose Modification

Dose modification can only occur after Week 4.

Subjects classified as clear at any of the on-treatment visits may stop the IP treatment at the investigator's discretion. They should remain in the trial and attend all visits up to and including the follow-up visit. The IP will continue to be dispensed to the subject, and IP treatment may be restarted at the subject's discretion. The subject should not discontinue treatment themselves between visits but is only allowed to stop using the IP treatment on the advice of the investigator at a scheduled visit.

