**MC2-01-C6_STATISTICAL ANALYSIS PLAN_Final 3.0_07 September 2020**
APPENDIX 1 TFLs Shells

MC2 Therapeutics

MC2-01-C6

Listing 16.2.5.2 Study Drug Compliance

Safety population

Page X of X

| Country/Site ID/ Subject ID | Age(Years) / Sex/Race/ Ethnicity | Visit | Was the subject diary completed by the patient (Reason, if Not Completed)? | Did the subject apply the study drug once daily to the scalp, trunk and/or limbs since the last visit? | Is the PGA "clear" and was the subject recommended to stop the treatment with study drug at the visit? | Was the treatment with study drug restarted by the subject after interruption at the last visit?/ Restart Date |
|-----------------------------|----------------------------------|----------|--|--|--|--|
| XXX/XX/XXXXX | 14/F/A/NHL | V2/Week2 | XXX | XXX | XXX | XXX/ YYYY-MM-DD |
| | | V3/Week4 | XXX | XXX | | ... |
| | | V5/Week8 | XXX | XXX | | |
| | | ... | ... | ... | | |

Country: CZE=Czech Republic, HUN=Hungary, DEU=Germany; Sex: F=Female, M=Male;

Race: A=Asian, B=Black or African American, W=White, O=Other; Ethnicity: HL=Hispanic or Latino, NHL=Not Hispanic or Latino.

Path to the program code, date and time of output/ Datasets used

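### Protocol 6.3 limits dose modification to after Week 4 yet, as worded, lets clear subjects stop at Week 2, so Week 4 HPA and calcium results can include subjects who are off IP

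*Protocol*

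**What the plan says.** Protocol 6.3 opens with a timing limit: "Dose modification can only occur after Week 4". The next sentence reads "Subjects classified as clear at any of the on-treatment visits may stop the IP treatment at the investigator's discretion". Such subjects stay under observation ("They should remain in the trial and attend all visits up to and including the follow-up visit"), continue to receive product, and "IP treatment may be restarted at the subject's discretion". Stopping is allowed only on the investigator's advice at a scheduled visit: "The subject should not discontinue treatment themselves between visits".

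Protocol 6.2, on individual areas, says "The subjects should therefore not continue treatment on a skin area which has been cleared" and refers to 6.3 for restarting.

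SAP 9.1 repeats the 6.3 sentences without linking them. SAP Table 14.1.1 lists being clear at any on-treatment visit as a reason for treatment discontinuation, with no Week 4 limit.

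**The concern.** The primary objective is the effect on the HPA axis and calcium metabolism under once-daily, maximum-use conditions, measured at Week 4 and Week 8. If a subject can stop at Week 2, the Week 4 tests may be done after a period off drug, during which any effect may have receded. Nothing in the primary analyses separates such a subject from those still applying the cream. The Week 4 suppression rate and the mean calcium changes could then look more favourable than they are for subjects on IP. Sites could also apply the two sentences differently.

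**Working it through.** **1. Can a stop fall before Week 4?** Protocol Table 7-1 schedules a PGA at Week 2, so a subject can be graded clear there. Protocol 6.3 ties stopping to scheduled visits, and Week 2 is the only one between Day 0 and Week 4. Nothing excludes it from the second sentence. The opening sentence, if it governs stopping, does exclude it. The text does not say which prevails.

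**2. Time off drug at the Week 4 tests.** Inputs: Week 2 is Day 14 ± 2 and Week 4 is Day 28 ± 2 (Table 7-1).
- Nominal: 28 − 14 = 14 days.
- Shortest: 26 − 16 = 10 days.
- Longest: 30 − 12 = 18 days.

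These run from the Week 2 visit. Under Protocol 6.2 the last application would be the morning before it, so the gap from last application is about one day longer.

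**3. Does the subject stay in the analysis?**
- HPA: the population requires Safety membership and normal function at SV2 (Protocol 8.3, SAP 6.2). The denominator is everyone tested at the visit (SAP 9.5).
- Calcium: Safety population (Protocol 8.3, SAP Table 14.3.4.2.1).
- Neither requires being on IP at Week 4. Only the PK population requires the Week 4 application.

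**4. Does compliance show it?** SAP 9.1: compliance = 100% × (required days − missed doses) / required days. Required days run from first to last application, less approved-stop days. With the Week 2 visit on SAP study day 15 and daily use on days 1 to 14, this is 100% × (14 − 0) / 14 = 100%.

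**5. Possible size for HPA.** The plan gives no target rate or precision to reproduce. The SAP method is Clopper-Pearson (SAP 7). With no events the upper 95% limit is 1 − 0.025^(1/n). The interim N is 7 (SAP 6.1). The number off IP is assumed, and all 7 are assumed tested.

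| Off IP at Week 4 | On IP | Upper limit, 0 suppressed | If 1 on-IP subject is suppressed |
|---|---|---|---|
| 0 | 7 | 1 − 0.025^(1/7) = 41.0% | 1/7 = 14.3% (0.4 to 57.9) |
| 1 | 6 | 1 − 0.025^(1/6) = 45.9% | 1/6 = 16.7% (0.4 to 64.1) |
| 2 | 5 | 1 − 0.025^(1/5) = 52.2% | 1/5 = 20.0% (0.5 to 71.6) |

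The all-subject row would show the n = 7 figures in every case. At the planned 30 subjects the same formula gives 11.6% for 0/30, 12.8% for 0/27 and 14.2% for 0/24.

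**6. Dilution.** If off-IP subjects are assumed to have fully recovered, observed rate = on-IP rate × (1 − fraction off IP). An on-IP rate of 20% would appear as 20% × 0.9 = 18%, 20% × 0.8 = 16% or 20% × 0.7 = 14% with 10%, 20% or 30% off. Full recovery is the extreme case; partial recovery dilutes less.

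**The case against.** The strongest reply is that 6.3 can be read consistently: the section opens with a timing limit and the rule for clear subjects operates inside it. Instructing all subjects to apply IP the day before Week 4, and planning an application at that visit, fits everyone being on drug until then. One could also hold that stopping is not a dose modification. Both readings are possible and neither is stated, so the need to reconcile stands.

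Second, the SAP does not hide approved stops. Table 14.1.1 counts them, Listing 16.2.5.1 gives last application and extent of exposure, Listing 16.2.5.2 gives restart dates, and Listing 16.2.5.3 dates approved-discontinuation days. With 7 subjects a reader could match these to the ACTH listing. This is correct and makes the gap smaller. It remains that the ACTH and calcium listings carry no IP status and no Week 4 primary table separates subjects by it.

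Third, the scenario may be rare: PGA 0 at Week 2 from at least moderate disease, investigator agreement and no restart. This stands; the documents give no frequency.

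Fourth, 6.2 and 6.3 collide only if every treated area clears between visits, since 6.2 speaks of an area and 6.3 of stopping treatment. That is a matter of fit, secondary to the main point.

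A reader might infer more than the documents support:
- *That the SAP plans for Week 2 stops, because the shell of Listing 16.2.5.2 has a Week 2 row under the column asking whether the PGA was clear and "was the subject recommended to stop the treatment with study drug at the visit".* The same row fills the cell on restart after an interruption at the previous visit. At Week 2 the previous visit is Day 0, so the entries are generic placeholders.
- *That a Week 2 stopper is certainly lost to the PK population, or certainly off drug for about 14 days.* Product is still dispensed and restart is left to the subject, so both are only possible.
- *That such a subject was unexposed.* There would have been about two weeks of exposure.

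**Conclusion.** The concern holds in limited form. As worded, Protocol 6.3 and SAP 9.1 leave open whether a clear subject may stop at Week 2. A subject who does so and does not restart counts in the Week 4 HPA and calcium results after a nominal 14 days off drug (10 to 18). This can dilute the Week 4 maximum-use result; the documents do not show that it has.

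The illustrated change in the upper limit, from 41.0% to 45.9% or 52.2%, rests on an assumed 1 or 2 of 7 subjects off IP and no suppression. All three limits are wide and the plan sets no threshold, so the issue is less the interval's width than which subjects it describes. Week 8 is a different matter: stops for clearance after Week 4 fit both sentences.

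**What to change.** 1. **Reconcile the text.** The sponsor must align the sentences in Protocol 6.3 and SAP 9.1, and their fit with Protocol 6.2 on cleared areas, so that sites have one rule. Which rule is a clinical decision not made here. The trial is halted for the interim analysis, so the protocol wording matters only if it is re-activated.
2. **Week 4, interim SAP.** Add IP status and date of last application to the ACTH and calcium listings. Show Week 4 HPA and calcium results for subjects on IP at that visit beside the all-subject rows, which stay as planned. Define on-IP status from the dosing data before the tables are run. SAP section 2 allows revision up to the interim database lock; after that, the rows should be identified as an addition and explained in the study report.
3. **Week 8.** Do not add an on-IP row. Protocol 7.6.2 takes subjects suppressed at Week 4 off the cream, so the row would exclude them and select for non-suppression. Instead, list off-IP subjects by reason (clear, suppressed, other) alongside the SAP's existing split by Week 4 suppression status.

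Cost: clarifying text, extra listing columns and one set of rows, from data already collected. The downsides are smaller denominators and a Week 4 on-IP row that leaves out early responders. That row is supportive only.

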6.4 Packaging, Labeling, Storage and Destruction

Medication labels for the IP will comply with the legal requirements of the country where the trial is performed and be printed in the local language.

The IP will be supplied by MC2s designated vendor and will be stored securely at the site under the control of the investigator. The temperature will be monitored and documented.

The MC2-01 cream will be supplied to the pharmacy/clinical site(s) as tubes containing 60 g of product. The MC2-01 cream is to be stored at a temperature of 2°- 8°C (35°- 46°F) at the site, and below 25°C (below 77°F) after dispensing to the subject. At all times, the MC2-01 cream should be protected from light.

All medication – unused and used - will be returned for reconciliation and destruction.

6.5 Assignment to Treatment

This is an open-label trial. All subjects who fulfil the trial eligibility requirements will be assigned to treatment with MC2-01. Hence, neither randomisation nor blinding will be performed.

6.6 Prior, Concomitant, and Prohibited Therapy

All medications, including over-the-counter (OTC) drugs and vitamins, herbal and dietary supplements, taken within 30 days prior to the start of the trial will be recorded at Screening. Thereafter, a record of all medications and supportive therapy taken during the course of the trial will be made. Information regarding the total daily dose, route of administration, start and discontinuation dates, and indication are to be recorded on the subject's eCRF.

6.6.1 Washout of prohibited medications prior to enrolment

A washout period must be completed if the subject has been treated with any medication as specified in the exclusion criteria ([Section 5.3](#)).

6.6.2 Prohibited medications during the trial

Use of any medication that would exclude the subject from participation in the trial (as specified in [Section 5.3](#) Exclusion Criteria) is also prohibited during the treatment and follow-up periods, which includes medications in the following categories:

- Use of biological psoriasis therapies;
- Use of oral systemic treatments with a possible effect on psoriasis (e.g., methotrexate, apremilast, retinoids, PDE4 inhibitors, corticosteroids, and other immunosuppressants).
- Use of phototherapy (PUVA and UVB).
- Use of topical treatments with a possible effect on psoriasis (e.g., corticosteroids, vitamin D analogs, retinoids, PDE4 inhibitors, salicylic acid, pimecrolimus, tacrolimus, anthralin, tar, etc.).
- Initiation of dosing or changes in dosage of drugs that are known to have an effect on psoriasis should be avoided. This includes, but is not limited to, beta-blockers, chloroquines, lithium, and ACE inhibitors.
- Use or initiation of estrogen and/or progestogen therapy (e.g. hormonal contraception).
- Use of strong systemic CYP 3A4 inhibitors (e.g., clarithromycin, telithromycin, nefazodone, itraconazole, ketoconazole, atazanavir, darunavir, indinavir, lopinavir, nelfinavir, ritonavir, saquinavir, tipranavir
- Emollients on the psoriasis affected areas.
- Any medications with proven or purported activity against psoriasis (including OTC medications) should be discussed with the Investigator prior to use.

6.6.3 Allowed treatment on the face, skin folds, and genital skin only

Subjects may receive laser treatment and use an emollient on the face, skin folds, and genital skin.

6.7 Treatment Compliance

Records of trial product used, and dosages administered will be kept during the trial. The trial monitor will note product accountability during site visits and at the completion of the trial.

At all on-treatment visits, the subject will be asked if he/she has used the medication as prescribed. If this is not the case, the degree and nature of noncompliance will be specified. In addition, subjects will be asked to complete a dosing diary during the treatment period (with assistance from the parent(s) or legal guardian(s), if needed) as a measure of treatment compliance. Subjects who are consistently noncompliant will be counseled.

Subjects will be asked to return all used and unused tubes in the outer box at each visit. All returned tubes that had been dispensed to a subject will be weighed to determine the amount of the IP used per treatment phase.

7.0 VISIT SCHEDULE AND ASSESSMENTS

Table 7-1 Visit Schedule and Assessments

	SV 1 ^a	SV 2	Visit 1	Visit 2	Visit 3	Visit 4	Visit 5	Follow-up Visit ^b
			Day 0	Week 2	Week 4	Week 6	Week 8	FU
Examination	Day -42 to Day -8	Day -7 to -4	Day 0	Day 14 ± 2	Day 28 ± 2	Day 42 ± 2	Day 56 ± 2	Day 70-84 ± 2
Informed assent/Informed consent ^c	X							
Inclusion/exclusion criteria	(X)		X					
Urine pregnancy test ^d	X		X					
Serum pregnancy test ^d		X			X		X	
Demographics, medical history	X							
Prior and concomitant medication	X	X	X	X	X	X	X	
Physical examination	X		X		X		X	X
PGA	(X)	(X)	X	X	X	X	X	
Body Surface Area (BSA) involvement	(X)	(X)	X		X		X	
Vital signs			X	X	X	X	X	
Laboratory assessments		X			X	(X) ^e	X	(X)
ACTH challenge test ^f		X			X		X	(X)
Morning urine assessment (second morning urine)	Instruct	X		Instruct	Instruct X	Instruct (X) ^g	Instruct X	(X)
Review food diary	Instruct	X		Instruct	Instruct X	Instruct (X) ^g	Instruct X	(X)
PK pre-dose blood sample (Single)		X	Instruct	X		Instruct	X	
PK serial blood samples ^h				Instruct	X			
12-Lead ECG		X			X		X	
Psoriasis Treatment Convenience Scale				X	X		X	
Dispense IP and diary for compliance			X	X	X	X		
Collect IP				X	X	X	X	
Compliance				X	X	X	X	
Adverse event(s) ⁱ		X	X	X	X	X	X	X
Local Skin Reactions			X	X	X	X	X	

- a) A washout period of up to 6 weeks must be completed if the subject has been treated with anti-psoriatic treatments or other relevant medication, as defined by exclusion criteria. There should be at least four days between SV1 and SV2 in order to keep the food diary for 4 days prior to SV2. Items denoted in **[brackets]** must be reviewed during screening, to assess if the subject is otherwise eligible. Such items must be checked for any change in eligibility status at Visit 1/Day 0 after the washout is completed.
- b) Follow-up visit is required 2 weeks after the Week 8 visit. For subject with HPA axis suppression at Week 8 the follow-up visit should be 4 weeks after the Week 8 visit. If the albumin-corrected serum calcium or the urinary calcium creatinine ratio is elevated at Week 8 a repeat test should be performed. In case of a repeat of the urinary calcium creatinine ratio the subject should be instructed to record the calcium intake 4 days prior to the visit.
For Czech Republic and Hungary: if an on-site visit is not required the follow-up visit can be a telephone call 2 weeks after Week 8 to ask for the wellbeing of the subject. In Germany an on-site follow-up visit is mandatory.
In addition, subjects discontinued due to a treatment-related AE will be monitored until the AE is resolved or until the medical condition of the subject is stable.
- c) Written informed assent must be provided by the subject and written informed consent must be provided by the parent(s), legal guardian(s) and the consent documents signed by the investigator or designee before any trial related procedures are carried out. For subjects requiring a washout period, informed assent/informed consent must be completed prior to washout.
- d) All female subjects.
- e) If serum albumin-corrected serum calcium is above the reference range at Week 4 a repeat test should be performed at Week 6.
- f) The ACTH challenge test must be performed between 7 and 9 am
- g) If the urinary calcium:creatinine ratio is above the reference range at Week 4, a repeat test should be performed, and the food diary filled in at Week 6. If the repeat test is also above the reference range, 24-hour urine collection must be performed.
- h) Blood samples for PK analysis are drawn before IP application (pre-dose sample) and 1, 3, and 5 hours after IP application.
- i) AEs are to be collected from the date of signing informed assent/informed consent and first trial-related activity is performed.

Instruct: At the indicated visits (Table 7-1), instruct the parent(s), legal guardian(s) or the subjects as to appropriate trial procedures as specified below:

- **Food diary:** instruct the parent(s), legal guardian(s) or subjects on how to use the food diary, especially recording their intake of calcium-rich nutrients. Consumption of calcium-rich foods should be kept constant during 4 days prior to each morning urine collection.
- **Second morning urine samples:** Second morning urine samples must be collected at the site on specific visits as specified in the visit schedule ([Table 7-1](#)). Food diary and morning urine sampling before Week 6 and Follow-up Visit is only relevant if urinary calcium:creatinine ratio is above the reference range at previous visit. Inform by telephone call a few days before the scheduled visit whether applicable or not.
- **IP application and PK blood samples:** instruct the parent(s), legal guardian(s) or subjects to apply the IP in the morning on the day before the Week 2, Week 4 and Week 8 visits. On the day of these visits, the subjects should not apply any IP before the visit. A reminder to the parent(s), legal guardian(s) or subjects may be needed a few days before the scheduled visit. If the subject has applied the IP in the morning prior to the visit, the visit must be rescheduled.

